### 4.2.2. Randomization Exclusion Criteria

- 1. Pneumonia due to COVID-19 or COVID-19—related hospitalization during Screening or Run in;
- 2. Use of the following medications during Screening or Run-in:
  - a. Neuroleptics, monoamine oxidase inhibitors, N-methyl-D-aspartate receptor ligand for pain (ketamine, amantadine, dextromethorphan [except low dose intermittent use for cough], memantine, methadone, dextropropoxyphene, and/or ketobemidone), and/or alpha-lipoic acid;
  - b. Tricyclic antidepressants and other tricyclic drugs including cyclobenzaprine and promethazine; triptans (prescribed usage outside of DPNP allowed); and/or 5-HT3 receptor antagonists;
  - c. Exposure of drugs or chemicals that may cause neuropathy and interfere with clinical evaluation. Agents include but are not limited to pyridoxine, hydralazine, metronidazole, phenytoin, dapsone, amiodarone, nitrofurantoin, paclitaxel, vinblastine, vincristine, cisplatin, etoposide, didanosine, disulfiram, suramin, zalcitabine, anti-tuberculosis medications (eg, isoniazid, rifampin, ethambutol, ethionamide), heavy metals, and industrial solvents;
  - d. Strong or moderate CYP3A4 inhibitors or inducers and P-gp inhibitors;
  - e. Topical pain medications intended to treat pain associated with DPNP (including but not limited to lidocaine 5% patch, over-the-counter capsaicin, amitriptyline, and/or isosorbide dinitrate spray);
  - f. Prescription patch containing 8% capsaicin;
  - g. Opioid use at a dose of ≥ 30 morphine milligram equivalents on 3 or more days per week during Screening or Run-in; or planned treatment with opioid or opioid-based drugs, including but not limited to tapentadol and/or tramadol throughout the course of the study;
  - h. Central nervous system active drugs detected in the urine such as cocaine, amphetamines, and cannabinoids (marijuana);
  - i. Oral prednisolone or equivalent.
- 3. Use of the following devices or procedures during Screening:
  - a. TENS unit for the treatment of DPNP;
  - b. Implanted neurostimulators;
  - c. Nerve decompression surgery or plans for such surgery for treatment of DPNP;
  - d. Steroid or local anesthetic nerve blocks;
  - e. Cryotherapy, intrathecal/epidural opioids, or botulinum toxin;
  - f. Alternative medicine products or treatments (eg, acupuncture, naturopathy, homeopathy, etc.);

g. Major surgery during Screening or planned to occur during the course of the study.

## 4.3. Protocol Waivers

Protocol waivers are not allowed. If there is an immediate hazard to a subject, the Investigator may deviate from the protocol using his/her best medical judgment to ensure the subject's safety. If such a deviation occurs, the site must notify the Sponsor and IRB within 48 hours.

## 4.4. Retesting and Rescreening

## 4.4.1. Retesting

Retesting is defined as repeating abnormal laboratory tests within the same study part.

Subjects who fail to qualify for the study based on an abnormal laboratory test may have any individual laboratory test retested once within the same study part at the discretion of the Investigator.

## 4.4.2. Screen Failures

Screen failures are defined as subjects who consent to participate in the clinical study but are not subsequently assigned to the study drug or entered in the study. A minimal set of screen failure information is required to ensure transparent reporting of screen failure subjects, to meet the Consolidated Standards of Reporting Trials (CONSORT) publishing requirements and to respond to queries from regulatory authorities. Minimal information includes demography, screen failure details, eligibility criteria, and any SAE. Individuals who do not meet the criteria for participation in this study (screen failure) may be rescreened in accordance with Section 4.4.3.

### 4.4.3. Rescreening

Subjects who fail to meet all Run-in inclusion/exclusion criteria may be considered for rescreening at the discretion of the Investigator after consultation with the Medical Monitor. These subjects will be considered Screen Failures.

Subjects may repeat Screening once to qualify for the study. If a subject is approved to rescreen, they will be given a new subject number and all screening procedures will be repeated.

Subjects who participate in the Run-in Period but fail to meet the Randomization criteria will not be allowed to rescreen for the study. These subjects will be considered Randomization Failures.

# 4.5. Subject Enrollment and Randomization

Following a Screening Period of up to 2 weeks, eligible subjects will be enrolled and enter a single-blind placebo Run-in Period (14± 2 days). Subjects in Part 1 who remain eligible (according to Randomization eligibility criteria) will be randomized 1:1:1 to either RTA 901 (10 or 80 mg) or placebo at Day 1, and subjects in Part 2 who remain eligible will be randomized 1:1:1 to either RTA 901 (Dose 1 or Dose 2) or placebo at Day 1 (see Table 3). Approximately 192 eligible subjects (64 subjects per treatment arm) will be enrolled in Part 1, and approximately 192 eligible subjects (64 subjects per treatment arm) will be enrolled in Part 2. Randomization within each part will be stratified using RTSM into 2 strata based on approved

SOC pain medication. One stratum will include subjects taking duloxetine, while the other stratum will include subjects taking pregabalin or gabapentin.

**Table 3:** Treatment Arms by Study Part

Study Part	Treatment Arms					
Part 1 (N=192)	10 mg RTA 901 (N=64)	80 mg RTA 901 (N=64)	Placebo (N=64)			
Part 2 (N=192)	Dose 1 RTA 901 (N=64) (selected from dose range of 1 to 80 mg) a	Dose 2 RTA 901 (N=64) (selected from dose range of 1 to 80 mg) a	Placebo (N=64)			

Abbreviations: E-R=exposure-response

## 4.5.1. Methods for Ensuring Blinding

In this 2-part, randomized, placebo-controlled, double-blind study, all subjects, Investigators, site personnel, and laboratories (except the bioanalytical laboratory) with direct involvement in the conduct of the study or their designees will be blinded to randomized treatment assignments. Subjects will be blinded throughout the study. Investigators will not be blinded in the single-blind Run-in Period but will be blinded in the double-blind Treatment Period of the study. To prevent potential bias, appropriate measures will be taken to ensure the blind is maintained for the subjects and personnel mentioned previously. To maintain the blind, Investigators will distribute blinded study drug kits to subjects as assigned by the RTSM (Section 7.3). The Data Monitoring Committee (DMC) will review unblinded safety data and make recommendations as appropriate. Members of the DSC will be unblinded to recommend Part 2 doses of RTA 901, respectively.

## 4.5.2. Methods for Unblinding

For subject unblinding, the Investigator is encouraged to contact the Medical Monitor to discuss situations in which he or she believes that the blind should be broken, but ultimately the Investigator has the right to break the blind (eg, in the event of a serious or life-threatening medical situation). If unblinding is required, the Investigator will utilize RTSM to perform the unblinding. If a study drug assignment is unblinded, the Investigator must describe the event that required unblinding in the subject's source documents. Subjects must discontinue taking the study drug if their treatment assignment has been unblinded to the Investigator (or designee). Such subjects must undergo the same study discontinuation procedures as those subjects who discontinue taking study drug for other reasons. Subject treatment assignments must not be unblinded in the case of an AE or SAE except as described above.

## 4.5.2.1. Unblinding for Regulatory Submission

In situations where regulation requires unblinding and reporting of a particular SAE, the appropriate bodies (eg, IRBs, regulatory agencies) must be provided with unblinded information according to the applicable regulatory requirement. This information must not be conveyed to any Investigator, site personnel or subject; therefore, this type of unblinding does not necessitate

<sup>a Dose selection in Part 2 will be determined by a Dose Selection Committee and based off an E-R analysis for efficacy from all subjects in Part 1.

that the subject discontinues taking study drug. In cases when unblinded information must be conveyed to local health authorities, the Clinical Program Operations and Data Management teams must be excluded.

## 4.5.2.2. Data Monitoring Committee

An independent DMC will review the accumulating unblinded safety data throughout the study and make recommendations as appropriate.

The DMC will consist of external experts supported by an independent statistical group which will prepare unblinded analyses for the DMC and will have no role in the Statistical Analysis Plan (SAP) after the study has started enrolling subjects. A separate statistical group not associated with the DMC will be responsible for producing and finalizing the SAP and executing the final data analysis of the study.

The DMC will be governed by a charter that will describe the following:

- Roles and responsibilities of the DMC members and the independent statistical group;
- Meeting format and frequency;
- Communication channels between the DMC, the independent statistical group, the Sponsor, and the blinded study statisticians;
- Voting process and requirements (eg, requirement of consensus for issuance of a termination recommendation);
- Provisions governing conflict of interest and confidentiality.

Briefly, the DMC will review the progress of the study and the accumulating unblinded safety data while the study is ongoing. The DMC will make recommendations to Sponsor representatives following each meeting. The DMC may recommend that the study continue as is, be modified to protect subject safety, or be terminated for safety. The DMC can make recommendations for the study based specifically on the analysis of the primary endpoint.

### 4.5.2.3. Dose Selection Committee

The DSC will be comprised of Sponsor personnel and an external pharmacometrics consultant. The E-R analysis will be conducted for efficacy using unblinded data from all subjects in Part 1, which is the basis for dosing recommendation of Part 2 to DSC. Eligible doses for selection in Part 2 will be limited to a dose range of 1 to 80 mg of RTA 901. The selected doses will be documented in a Note-to-File to the Investigators and IRBs (as appropriate) and will not require a protocol amendment.

Details of the membership, objectives, and process to be followed by the DSC will be described in a separate charter. Additionally, a separate data management and analysis plan supporting this activity will be created. Results will be reported in a separate standalone report, outside the CSR.

## 4.6. Study Drug Discontinuation, Interruption, and Subject Termination

## 4.6.1. Discontinuation of Study Drug

Discontinuation from study drug does not mean discontinuation from the study. Subjects who discontinue the study drug early for any reason should complete the procedures associated with the Week 12/EOT visit at the closest study visit. If the subject discontinued study drug during a study visit, the EOT procedures should be performed during that study visit. If the subject discontinues study drug in between visits, he/she will perform the EOT procedures at the next scheduled study visit. The subject will then complete the procedures associated with the Week 16/end of study (EOS) visit 4 weeks after discontinuation.

If a clinically significant (CS) finding is identified (including, but not limited to changes from baseline) after enrollment, the Investigator or qualified designee will determine if any change in subject management is needed. Any new clinically relevant finding will be reported as an AE.

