# 3.5. Follow-up/End of Study (Week 16)

The Follow-up Period includes 1 clinic visit on Day  $113 \pm 2$ , which must occur approximately 4 weeks following the EOT visit. Procedures will be performed according to the Schedule of Assessments (Table 4). Completion of this visit concludes the subject's participation in the study.

Subjects will be directed to continue completing the NPRS and recording their rescue medication usage in the e-diary at bedtime. Upon waking, subjects will be asked to complete the DSIS.

Additional procedures are to be completed according to the Schedule of Assessments (Table 4).

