d Subjects who discontinue study drug early for any reason should complete the procedures associated with the Week 12/EOT visit at the nearest study visit and the Follow-up Week 16/EOS visit 4 weeks later.

e Run-in eligibility procedures do not need to be repeated at the Run-in visit; however, a review of any changes in eligibility criteria should be evaluated prior to Run-in visit procedures.

f Adverse event assessments should be performed after the informed consent has been signed.

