3.1.3. Analysis Visit Windows

Data from early termination visits and unscheduled visits will be assigned to an appropriate scheduled postbaseline visit using a windowing scheme for assessments that are tabulated or summarized by visit. Scheduled visits will not be windowed.

Numeric pain rating scale (NPRS) and daily sleep interference scale (DSIS) are collected daily using an e-diary form. The daily scores will be mapped to an analysis "Week" according to the following windows defined by Study Day in conjunction with study phases described above. Subjects are instructed to report the NPRS number that best indicates the average intensity of neuropathic pain over the last 24 hours throughout the study daily at bedtime. Subjects also complete the DSIS via their e-diary daily upon waking.

The weekly mean is defined as the sum of non-missing daily scores divided by the number of days with non-missing scores for that week. Subjects with fewer than 3 daily scores during an analysis week will be considered to have a missing weekly mean for that week.

The analysis window for efficacy endpoints will be defined based on the schematic as follows:

Table 2: Analysis Visit Window for weekly NPRS average pain intensity

Visit	Lower Bound in Study Day (inclusive)	Upper Bound in Study Day (inclusive)
Run-in period	First record during run-in period	-1
Randomized/treatm	ent period	
Baseline	-7	-1
Week 1	1	7
Week 2	8	14
Week 3	15	21
Week 4	22	28
Week 5	29	35
Week 6	36	42
Week 7	43	49
Week 8	50	56

Week 9	57	63				
Week 10	64	70				
Week 11	71	77				
Week 12 (EOT)	78	84				
Follow-up period						
Week 13	85	91				
Week 14	92	98				
Week 15	99	105				
Week 16 (EOS)	106	112				
Week 16 (EOS)	106	112				

Note1: the NPRS number that best indicates the average intensity of neuropathic pain over the last 24 hours throughout the study daily at bedtime, recorded using e-dairy.

Note 2: Run-in visit is intended to describe run-in phase average pain score prior to first dosing in randomized phase.

Note 3: All available data will be used to calculate the weekly average mean up to Week 12 regardless of treatment discontinuation per ITT principle.

Note 4: If the last study dose for a patient is beyond the defined windowing for Week 12, only off study treatment days will be used to calculate off study treatment follow-up weekly mean.

Table 3: Analysis Visit Window for DSIS

Visit	Lower Bound in Study Day (inclusive)	Upper Bound in Study Day (inclusive)			

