3.3. Study Periods

3.3.1. Screening Period (Days -28 to -15)

The Screening Period Includes 1 clinic visit up to 2 weeks prior to the Run-in Period (within 28 $[\pm 2]$ days prior to Day 1). Daily NPRS and DSIS will be collected using an e-diary from Screening to the end-of-study visit. Washout from prohibited medications is allowed if the Investigator deems it medically appropriate; the washout period must cover 5 half-lives of the prohibited medication and must be completed prior to the last 7 days of Screening.

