6.2. Multiplicity Control

A sequential stepwise testing will be performed on the primary endpoint for RTA 901 group (80mg, 10mg) compared to placebo in the following testing order to control the overall type I error at two-sided alpha level of 0.05:

- Step 1: Comparison of 80 mg group versus placebo group. If p-value <0.05, then proceed to Step 2. If not, testing for subsequent step is considered as exploratory.
- Step 2: Comparison of 10 mg group versus placebo group.

No formal testing will be performed for the secondary endpoints.

6.3. Primary endpoint of change from baseline in NPRS average pain intensity at week 12

The primary endpoint is the change from baseline in the average daily NPRS pain intensity score during Week 12.

The NPRS of pain intensity is a numeric scale, ranging from 0 (representing no pain at all) to 10 (representing the worst pain imaginable). The subject selects a whole number (0 to 10) that best indicates the intensity of their neuropathic pain in the past 24 hours. Subjects will report how they perceive their average neuropathic pain intensity during the past 24 hours at bedtime.

The weekly mean is defined as the sum of non-missing daily scores divided by the number of days with non-missing scores for that week. Subjects with fewer than 3 daily scores during an analysis week will be considered to have a missing weekly average for that week.

No imputation will be conducted at weekly mean level.

The MMRM model will include baseline NPRS score, visit, treatment, the interaction of treatment and visit, the interaction of baseline NPRS score and visit. The analysis visit will include all visits (study week) up to week 12 during double-blinded treatment period. An unstructured covariance (UN) matrix will be used to model the within-subject variability. Model convergence will be checked. If the unstructured covariance model fails to converge with the Newton-Raphson algorithm after increasing the default maximum iterations, the Fisher scoring algorithm will be used to provide initial values of the covariance parameters.

If the model does not converge with an unstructured covariance matrix, then the analysis visit will include weeks 1, 2, 4, 6, 8, 10 and 12 per protocol scheduled assessment visits.

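### For subjects who stop study drug in about the first half of treatment, the Week 12 pain mean cannot be collected by design, and no readable sensitivity analysis shows how far the mean difference could move.

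*Protocol*

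**What the plan says.** **Visits after an early stop.** Protocol 4.6.1 separates stopping drug from leaving the study but brings the closing visits forward. On EOT: "If the subject discontinues study drug in between visits, he/she will perform the EOT procedures at the next scheduled study visit". On EOS: "The subject will then complete the procedures associated with the Week 16/end of study (EOS) visit 4 weeks after discontinuation". Protocol Table 4 footnote d, repeated in SAP Table 1, counts differently. It asks the subject to "complete the procedures associated with the Week 12/EOT visit at the nearest study visit and the Follow-up Week 16/EOS visit 4 weeks later".

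**End of the diary.** Protocol 3.5 says of the EOS visit: "Completion of this visit concludes the subject's participation in the study". SAP 3.3.1, like the protocol synopsis, says: "Daily NPRS and DSIS will be collected using an e-diary from Screening to the end-of-study visit".

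**What is analysed.** SAP Table 2 sets Week 12 as Days 78–84. Note 3 to that table says: "All available data will be used to calculate the weekly average mean up to Week 12 regardless of treatment discontinuation per ITT principle". SAP 3.1.3 adds: "Subjects with fewer than 3 daily scores during an analysis week will be considered to have a missing weekly mean for that week". SAP 6.3 specifies an MMRM and states: "No imputation will be conducted at weekly mean level". Its readable sensitivity analyses are the same MMRM in the per-protocol set, an analysis dropping data after treatment discontinuation, and an MMRM extended to Week 16. SAP 6.4.1 and 6.4.2 count a missing Week 12 mean as non-response, but only for the responder endpoints and the responder curve.

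**The concern.** The SAP aims at Week 12 pain whether or not the subject is still on drug. For an early stopper who follows the protocol fully, that value is never recorded. The MMRM imputes nothing. It estimates the Week 12 means as if, given the observed weeks, the missing values behaved like the observed ones. The SAP does not use the term missing at random, but a likelihood MMRM without imputation relies on it.

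The three sensitivity analyses of the mean share that assumption. The Week 16 model adds nothing for these subjects, because their diaries close by about Day 79 at the latest and they have no Week 13–16 scores either. The formal tests rest on this mean difference, with 80 mg gating 10 mg. For a result near the boundary, a reader would want to know how much worse the unseen values must be to change the conclusion.

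Pain-related stopping is also plausible from the text. Under Protocol 7.8.3, some subjects on ibuprofen rescue who cannot keep to the revised conditions must stop treatment and withdraw, which ties missingness to rescue need.

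**Working it through.** **1. The plan's own figure.** SAP 2.4: difference 1.2, SD 2.4, 64 per arm, two-sided 0.05. The two-sample t-test gives 80.2% power, so the stated 80% reproduces. SE = 2.4 × √(2/64) = 0.424. The smallest significant difference is 1.979 × 0.424 = 0.840.

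**2. Which stops lose Week 12.** Visits fall on Days 8, 15, 29, 43, 57, 71 and 85, each ±2. I count a score on the EOS day.

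| Stop day | EOS = stop + 28 | Scores in Days 78–84 | EOS = next visit + 28 | Scores in Days 78–84 |
|---|---|---|---|---|
| 43 | 71 | 0 | 71 | 0 |
| 44 | 72 | 0 | 85 | 7 |
| 49 | 77 | 0 | 85 | 7 |
| 50 | 78 | 1 | 85 | 7 |
| 51 | 79 | 2 | 85 | 7 |
| 52 | 80 | 3 | 85 | 7 |

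The last stop day without a valid mean is 51 under Section 4.6.1 (49–53 with ±2 days on EOS), or 43 under the footnote with EOT at the next scheduled visit (41–45 with the Week 6 window). For stops on Days 50–51 the diary ends inside Week 12, with too few scores. Reading the footnote's nearest visit literally gives about Day 50.

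**3. How many subjects.** No stop rate is documented. Assuming 20% of an arm stops, evenly over Days 1–84, the share without a Week 12 mean is 0.20 × 51/84 = 0.121 (7.8 of 64) or 0.20 × 43/84 = 0.102 (6.6 of 64).

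**4. Bias under assumed conditions.** The simulation used 60,000 per arm and 12 weekly values, with correlation r^lag. The effect of 1.2 built over 4 weeks and was lost over 2 or 8 weeks off drug. Stops were unrelated to pain, EOS was at stop + 28, and the estimate was maximum likelihood as in an MMRM, compared with full data. Overstatement for 2-week / 8-week loss:

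| Active/placebo stops | r = 0.95 | r = 0.85 | r = 0.70 |
|---|---|---|---|
| 10%/5% | 1.0 / 2.5% | 2.8 / 3.6% | 4.3 / 4.5% |
| 20%/10% | 1.4 / 4.9% | 5.3 / 7.2% | 8.7 / 9.1% |
| 30%/15% | 1.4 / 7.5% | 8.0 / 11.4% | 13.9 / 14.7% |

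These are rough: a separate run with 30,000 per arm gave 6.1 / 7.9% at 20%/10% and r = 0.85. Compound symmetry, which SAP 6.3 says was assumed for sample size, gives about 7–10% at 20%/10%. Overall the range is about 1–15%, or 0.01–0.15 points.

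- No drug effect, stops unrelated to pain: within 0.01 points of zero.
- Only 75% of stoppers return the diary: 6–9% (20%/10%) and 9–14% (30%/15%) at r = 0.95–0.85.
- Placebo stops (20%) rising with the subject's own Week 12 pain, active stops (10%) not: the effect is understated by 4–11% (0.05–0.12 points).

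**5. How much worse the unseen values must be.** Each NPRS point by which the active-arm missing values are worse than modelled lowers the difference by 0.102–0.121.

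- With the full-64 SE: (1.2 − 0.840)/0.121 = 3.0 and (1.2 − 0.840)/0.102 = 3.5. For an observed 0.95, 0.110/0.121 = 0.9 and 0.110/0.102 = 1.1.
- With a completers' SE at the Day 51 cut-off and 20% stops in both arms: n = 64 × 0.879 = 56.2 per arm, SE = 2.4 × √(2/56.2) = 0.453, critical difference about 0.897. Then (1.2 − 0.897)/0.121 = 2.5 and (0.95 − 0.897)/0.121 = 0.4.

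The MMRM's SE should lie between. So roughly 2.5–3.5 points would overturn an observed 1.2, and roughly 0.4–1.1 points an observed 0.95.

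**The case against.** **The effect is small.** At most 0.15 points against an SE of 0.42 is about a third of one standard error. Part 1 exists to inform Part 2 doses, and those rest on an exposure-response analysis with its own plan, which is not among these documents. No effect on that decision is shown. This stands and limits the priority.

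**The sponsor chose this.** The change summaries for Versions 2 and 3 show a deliberate decision that stoppers attend only EOT and EOS. That stands for clinic visits. Those entries do not address the home diary.

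**The planned outputs are not silent.** SAP 5.2 tabulates discontinuation reasons. Comparing the primary MMRM with the analysis excluding post-discontinuation data shows how far the collected off-drug scores move the mean. The responder models and curve treat missing as failure. A reader might infer that the plan gives no information on missing data, and that would go too far. But these outputs are indirect or on another scale, and none replaces a direct check on the mean difference.

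**A stronger reading.** A reader might also infer that the gap creates a false positive or invalidates the primary analysis. The documents do not support that. With no drug effect and stops unrelated to pain the bias is about zero, and with pain-related stopping the direction can reverse. Parts of the SAP are blacked out, so the statement about sensitivity analyses covers only the readable text.

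**Conclusion.** The gap is real and follows from the documents alone: the Week 12 mean is uncollectable for stops through about Day 51 or about Day 43, depending on which EOS rule is followed, and the two rules disagree for stops between visits. The cut-offs need no outside assumption beyond the diary being filled in up to EOS. The size does: it rests on assumed stop rates, an effect that fades off drug, and the correlation pattern. On those assumptions the primary estimate is modestly too favourable. A clear result would be hard to overturn and a borderline one much less so, and no readable planned analysis would quantify which applies. This is a worthwhile low-cost improvement of modest priority.

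**What to change.** 1. Reconcile the EOS timing for drug discontinuers in Protocol 4.6.1 with footnote d of Protocol Table 4 and SAP Table 1.
2. In Protocol 4.6.1, ask subjects who stop study drug but have not withdrawn consent to continue the home e-diary through Day 84, with no added clinic visits. The synopsis, Protocol 3.5 and SAP 3.3.1 must change to match, since they end the diary or participation at EOS. State how adverse events learned of in that time are handled, because collection under Protocol 6.1 may already have closed. At r = 0.95–0.85 and 20%/10% stops, 75% diary return to Day 84 cuts the overstatement from 6.0–8.9% to 2.9–4.5%, and full return removes it.
3. In SAP 6.3, keep every planned analysis and add a delta-adjusted (tipping-point) sensitivity analysis of the Week 12 NPRS change. This also covers subjects who withdraw altogether. Reference-based imputation is optional and should not be called conservative in every case.

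Cost: a short amendment with IRB approval (Protocol 10.5), some diary burden, one extra analysis, and possibly a less favourable estimate. SAP 6.1 already reports a count among randomised patients, so Part 1 was well advanced. The diary change therefore mainly serves Part 2, which gets its own SAP, and any Part 1 subjects still in follow-up. The added analysis serves Part 1 without new data.
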